### **7.3.4 Safety analyses**

Adverse events will be coded using the Medical Dictionary for Regulatory Activities (MedDRA). Standard BI summary tables and listings will be produced. All adverse events with an onset between start of treatment and end of the residual effect period (REP), a period of 7 days after the last dose of trial medication, will be assigned to the on-treatment period (see above) for evaluation.

All treated patients will be included in the safety analysis. In general, safety analyses will be descriptive in nature and will be based on BI standards. No hypothesis testing is planned.

Statistical analysis and reporting of adverse events will concentrate on treatment-emergent adverse events, i.e. all adverse events occurring between start of treatment and end of the

residual effect period. Adverse events that start before first drug intake and deteriorate under treatment will also be considered as ‘treatment-emergent’.

Frequency, severity, and causal relationship of adverse events will be tabulated by system organ class and preferred term after coding according to the current version of MedDRA at the database lock.

Laboratory data will be analysed both quantitatively as well as qualitatively. The latter will be done via comparison of laboratory data to their reference ranges. Values outside the reference range as well as values defined as clinically relevant will be summarised. Treatment groups will be compared descriptively with regard to distribution parameters as well as with regard to frequency and percentage of patients with abnormal values or clinically relevant abnormal values.

Vital signs, physical examinations, or other safety-relevant data observed at screening, baseline, during the course of the trial and at the end-of-trial evaluation will be assessed with regard to possible changes compared to findings before start of treatment.

#### Withdrawal/taper period

As described in [Section 3.1](#), during the initial randomisation phase, patients will be randomised to either BI 409306 50 mg qd and either abrupt withdrawal or slow taper, or BI 409306 25 mg qd and either abrupt withdrawal or slow taper, or Placebo. This 7-day, post 28-week treatment, withdrawal/taper period will assess the impact of abrupt withdrawal versus slow taper of study drug to assess drug dependency, and does not affect the primary 28-week analysis, for which the doses will be pooled and the assignment to taper vs. withdrawal during randomisation will not be taken into account.

Contrary to the primary analysis, in which the randomisation to a withdrawal/taper group will be ignored, this safety analysis will assess the following:

- Change in vital signs
- Change in suicidality
- Adverse events

The analyses will be descriptive only and will be performed only on patients who were randomised to an active treatment arm and will include three different comparisons, which will be analysed hierarchically:

1. the effect of tapering versus abrupt withdrawal when both doses are pooled.

If an effect is apparent, then the next evaluation will be:

2. the effect of dose dependency

and finally,

3. the interaction between dose dependency and the withdrawal/taper.

All these analyses will only use the data obtained during the withdrawal/taper period.

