Day 7 1 tablet in P.M.	1 x 10 mg placebo tablet	1 x 10 mg placebo tablet	1 x 10 mg BI 409306 tablet	1 x 10 mg placebo tablet	1 x 10 mg BI 409306 tablet

Administration of study drug tablets will be in the evening, preferably just before going to bed. The most common side effects with the use of BI 409306 are visual adverse events occurring at maximum concentration ( $C_{max}$ ) (30-40 min post-dose). By taking the study drug at bedtime, the negative effect, if any, of experiencing these side effects is expected to be minimized.

Patients should be instructed to take their study medication with water at approximately the same time in the evening, with or without food. BI 409306 tablets should not be chewed or crushed. If a dose is missed by more than 12 hours, that dose should be skipped and the next dose should be taken as scheduled.

A dose reduction of BI 409306 is not possible.

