7.8.5 Others

Taper/withdrawal (T/W) period

The 7-day, post 28 week treatment T/W period will not be analyzed as part of the primary analyses. Planned analyses on the T/W period will be descriptive only

Vital signs, suicidality and adverse events will be closely monitored during this period T/W. Only data obtained during the T/W period will be included in the analyses, and only of those patients randomized to the active treatment arms will be included in comparisons, which include all tapering comparing to all withdrawal as well as comparisons between the individual doses.

IDEA for CON.

TSAP for BI Trial No: 1289-0049 Page 32 of 35

[figure not shown]
Proprietary confidential information © 2021 Boehringer Ingelheim International GmbH or one or more of its affiliated companies

8. **REFERENCES**

1.	CPMP/ICH/363/96: "Statistical Principles for Clinical Trials", ICH Guideline Topic E9, Note For Guidance on Statistical Principles for Clinical Trials, current version.
2.	001-MCS 36-472: "Standards and processes for analyses performed within Clinical Pharmacokinetics/Pharmacodynamics", current version; IDEA for CON.
3.	001-MCG-156_RD-01: "Handling of missing and incomplete AE dates", current version; IDEA for CON.
4.	001-MCG-156: "Handling and summarization of adverse event data for clinical trial reports and integrated summaries", current version; IDEA for CON.
5.	CPMP/ICH/137/95: "Structure and Content of Clinical Study Reports", ICH Guideline Topic E3; Note For Guidance on Structure and Content of Clinical Study Reports, current version
6.	001-MCG-157: "Handling, Display and Analysis of Laboratory Data", current version;

TSAP for BI Trial No: 1289-0049 Page 33 of 35

Proprietary confidential information © 2021 Boehringer Ingelheim International GmbH or one or more of its affiliated companies

Proprietary confidential information © 2021 Boehringer Ingelheim International GmbH or one or more of its affiliated companies

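### The taper-versus-withdrawal comparison leaves out placebo and all data after the 7-day period, so it has no background rate and cannot separate delayed from prevented symptoms

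*Protocol*

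**What the plan says.** Protocol 7.3.4 (Withdrawal/taper period) gives the purpose of the week after the 28-week treatment period: it "will assess the impact of abrupt withdrawal versus slow taper of study drug to assess drug dependency". The outcomes are vital signs, suicidality and adverse events (AEs). The analysis is descriptive, "will be performed only on patients who were randomised to an active treatment arm", and is confined to the period itself: "All these analyses will only use the data obtained during the withdrawal/taper period". It starts with taper against withdrawal, doses pooled. On dose it adds a condition: "If an effect is apparent, then the next evaluation will be".

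SAP 7.8.5 repeats the window ("Only data obtained during the T/W period will be included in the analyses") and the restriction to active arms. It lists "all tapering comparing to all withdrawal as well as comparisons between the individual doses" without restating the condition on dose.

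Other parts of the plan bear on this:

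- Protocol 7.6 and SAP 6.1 randomise placebo patients to taper or withdrawal as well, and they go through the same week.
- Protocol Table 4.1.4: 2 gives abrupt-withdrawal patients placebo tablets from Day 1. Taper patients still take "1 x 10 mg BI 409306 tablet" on Day 7. On timing, "Administration of study drug tablets will be in the evening".
- The Flow Chart places visits at Visit 16 + 2, + 4 and + 7 (each with a window of one day either side), then follow-up at Visit 16 + 28.

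**The concern.** A dependency assessment should show whether stopping the drug produces more symptoms than would occur anyway, and whether a taper changes that. The planned comparison sets patients who are off drug against patients who are still being dosed, within one week and without the placebo patients who could supply the background.

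This leaves two results open to more than one reading. If the modes look alike, the shared rate may be ordinary background, or both modes may be equally raised. If taper looks better, it may have prevented symptoms or moved them past Day 7. At stake is what the trial can later be cited for on how to stop the drug.

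**Working it through.** The plan gives no event rate, sample size or precision for this comparison, so there is no figure of its own to reproduce. The check is a count of days and visits from Protocol Table 4.1.4: 2 and the Flow Chart.

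**Exposure of taper patients in the window**

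- 25 mg arm: 20+20+20+10+10+10+10 = 100 mg, against 7 × 25 = 175 mg at full dose (57%).
- 50 mg arm: 40+30+30+20+20+10+10 = 160 mg, against 7 × 50 = 350 mg (46%).

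**Share of drug-free days used, up to Visit 16 + 28**

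Share = (abrupt days in window + taper days in window) / (all abrupt days + all taper days), for one patient per mode.

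- Taper Day 7 counted as Visit 16 + 7: abrupt 7 of 28, taper 0 of 21. (7+0)/(28+21) = 7/49 = 14%.
- Evening dosing counted alike in both modes (last active dose at Visit 16 − 1 for abrupt and Visit 16 + 6 for taper): abrupt 8 of 29, taper 1 of 22. 9/51 = 18%.
- The same, with Visit 19 one day late: abrupt 9, taper 2. 11/51 = 22%.

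**What the general treatment-emergent AE tables add**

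They include placebo, but SAP 6.1 pools modes by dose in most analyses. Their coverage depends on which last dose is meant.

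- Seven days after the last active dose (the on-treatment period as spelled out in Protocol 7.3 and SAP 6.1): (7+7)/49 = 14/49 = 29%.
- Seven days after the last blinded tablet (a possible reading of Protocol 7.3.4 and SAP 7.8.1, since abrupt patients take tablets through Day 7): (14+7)/49 = 21/49 = 43%.

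Under SAP 7.8.1, later AEs are listed only.

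**Visits in the first 7 drug-free days**

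There are about 3 after abrupt withdrawal (+ 2, + 4, + 7). After taper there is at most 1: Visit 19, within about the first drug-free day. The next visit is at + 28.

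**Illustration with assumed rates (not in the documents)**

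Let b be the background risk per week and w the extra risk, all of it falling in the 7 days after the last active dose. Take b = 5% and w = 10%.

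- Seven-day window: abrupt 1 − 0.95 × 0.90 = 14.5%, taper 5.0%. The result is the same whether taper delays or prevents.
- To Visit 16 + 28: four-week background 1 − 0.95⁴ = 18.5%. Abrupt 1 − 0.95⁴ × 0.90 = 26.7%. Taper is 26.7% if symptoms are delayed and 18.5% if they are prevented.
- With b and w each at 5% or 10%, the 7-day difference is 4.5 to 9.5 points in both cases. At Visit 16 + 28 it is 0 if delayed and 3.3 to 8.2 points if prevented.

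**Precision at planned size**

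Protocol 7.7 plans 258 active and 129 placebo patients with 20% dropout. That gives 258/2 × 0.8 ≈ 103 per mode and 129 × 0.8 ≈ 103 on placebo. At assumed event rates of 5%, 10% and 20%, the 95% half-width is 1.96 × √(2p(1−p)/103) = 5.9, 8.2 and 10.9 points for the difference between modes. For the placebo rate it is 1.96 × √(p(1−p)/103) = 4.2, 5.8 and 7.7 points. SAP section 4 says recruitment stopped early, so the real groups are smaller and the intervals wider.

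**The case against.** The strongest defence is that the plan never asks whether taper prevents or delays symptoms. Protocol 3.2 speaks of monitoring for withdrawal signs. A randomised, blinded comparison of patients off drug with patients still partly dosed addresses that directly, and all of it is descriptive. This stands as far as acute effects go. A reader might infer that the comparison is invalid or confounded; it is not.

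Counting days to Visit 16 + 28 may overstate the loss, because the plan's own residual-effect period is 7 days. If only the first 7 drug-free days in each mode are counted, the comparison covers 7 of 14 (50%) and the general AE tables cover all 14. That is a fair alternative. The missing half, however, is the whole of the taper arm's drug-free week, and the general tables mostly do not separate the modes. Protocol 4.1.2 also regards 10 mg as too low to be therapeutic. Treating the 10 mg days as off drug (4 of 7 and 2 of 7, mean 3) gives (7+3)/(28+24) = 10/52 = 19%, inside the range above.

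Existing outputs narrow the gap. General safety summaries (Protocol 7.3.4) follow vital signs to the end of the trial, though not expressly by mode. The Full follow-up relapse analysis (SAP 7.4.2) includes placebo, but not mode. SAP 7.8.5 restricts who enters comparisons and does not expressly bar a placebo display, but the protocol restricts the analyses themselves. Some SAP sections are not in the public text and may hold a by-mode output.

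A reader might also infer that a dose effect would go unexamined if no mode effect were seen. The documents do not support that: the later SAP lists dose comparisons without the condition, and in a descriptive analysis the condition controls no error rate. It is a minor point of wording.

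**Conclusion.** The point holds as an optional improvement to a descriptive safety analysis. The planned table can show acute effects of abrupt cessation in the 7-day period. It cannot give a background rate, and it cannot tell prevention from delay. It uses about 14% of drug-free days on the simplest count, or 18% to 22% once evening dosing and a late Visit 19 are allowed for. The general AE tables reach 29% or 43%, largely without mode. These figures assume one completing patient per mode with visits on schedule, except where stated.

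A reader might infer that extending the tables to follow-up would settle prevention against delay. It would not fully do so. Three visits fall in Days 1 to 7 and none between Visit 16 + 7 and Visit 16 + 28, so delayed symptoms after taper are less well ascertained even when both modes share a calendar. A similar total in both modes would support delay. A lower total after taper would not by itself prove prevention.

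Nor are the data missing: only the analysis is restricted. The primary analysis ignores mode and excludes this period, so it is untouched.

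**What to change.** - Keep the 7-day table and add placebo (taper and withdrawal) as a descriptive reference.
- Remove the in-period restriction for AEs. Tabulate onset from Visit 16 to the follow-up visit, by mode and with placebo, for Days 1–7, Day 8 to follow-up, and both combined. Placebo in the same calendar period gives the background at equal visit frequency.
- Show follow-up C-SSRS and vital signs by mode as single-timepoint summaries.
- Footnote every display, calendar-period ones included, with the visit pattern and its effect on capturing delayed symptoms.
- State whether the residual-effect period runs from the last active dose or from the last blinded tablet.

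The cost is a few descriptive tables. Protocol 5.2.6.2 already collects AEs to each patient's end of trial, and Protocol 8.3.1 makes the onset date mandatory. The Flow Chart schedules C-SSRS and vital signs at follow-up. No new visit or test is needed.

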### 7.3.5 Pharmacokinetic and pharmacodynamic analyses

The relationship between the BI 409306 plasma concentrations and efficacy response and AE may be assessed descriptively.

In case the primary analysis demonstrates a drug effect, PK analysis on all plasma concentrations will be performed by population PK and PK/PD modelling (i.e. exposure-response). These pharmacometric analyses, if performed, will be reported separately.

### 7.4 INTERIM ANALYSES

No interim analysis is planned but blinded evaluation of the relapse rate will be conducted on an ongoing basis and blinded sample size re-calculations may be performed.

### 7.5 HANDLING OF MISSING DATA

All patients will be followed up for relapse to the greatest possible extent as described in [Section 3.3.4.1](#). Any patient who has not relapsed will be censored in the analysis of the primary endpoint at the time of last patient contact. For any secondary analysis using RRR, all patients in the FAS will be included in the calculation of the RRR, regardless of dropout.

For the key secondary analyses, if a patient misses a visit, the data will not be imputed. The mixed effects model will handle missing data based on a likelihood method under the “missing at random” assumption.

Further details about handling missing data will be specified in the TSAP.

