### 7.3 PLANNED ANALYSES

Two patient populations are defined:

- The treated set (TS) includes all patients who were dispensed study medication and were documented to have taken at least one dose of investigational treatment
- The full analysis set (FAS) includes all patients in the treated set with at least one post-baseline measurement of any type

No per protocol population will be used for analyses; however protocol violations will be identified and listed.

Analysis sets will be fully defined in TSAP.

Three analysis periods are defined:

- **Intent to Treat (ITT) follow-up:** from treatment start date until the end of the intended complete treatment period:

For patients who complete the trial according to the [flow chart](#), the withdrawal/taper period is not included. Additionally, if a patient happens to take drug for 29 weeks (i.e. 1 week longer than the planned 28 weeks) and then begin the withdrawal/taper period, the withdrawal/taper period will not be included.

For patients who discontinue prior to the 28 week treatment period, e.g. at week 25, the follow-up period until the end of week 28, is included.

- **Full follow-up:** from randomisation until the end of the trial, including all observed time on and off trial medication until the follow-up visit or the last date of contact:

For patients who discontinue trial medication according to the [flow chart](#), the withdrawal/taper period is included. Additionally, if a patient happens to take drug for 29 weeks (i.e. 1 week longer than the planned 28 weeks) and then begin the withdrawal/taper period, the withdrawal/taper period is included.

For patients who discontinue prior to the 28 week treatment period, e.g. at week 25, the follow-up period until the last contact date is included.

The full follow-up analysis period will be used as a sensitivity analysis to the ITT follow-up analysis.

- **On-treatment:** from treatment start date until the date of discontinuation of trial medication + 7 days:

For all patients this analysis period includes only the time on trial medication + 7 days after taken off trial medication.

For patients randomised to the withdrawal period, this will include 28 weeks of treatment, or for early discontinued patients, the time period on active treatment prior to discontinuation + 7 days, which corresponds to the 7 days abrupt withdrawal period.

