### Secondary analysis

Time to change in antipsychotic medication will be analysed in the same manner as the primary endpoint using the stratified Cox proportional hazards model.

Additionally, the analyses for suicidal ideation and behaviour as assessed by C-SSRS will be analysed by calculating a relative risk reduction and providing a 95% confidence interval around the RRR.

The PGI-I score, change in CGI-S and PSP will be summarized descriptively.

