4. CHANGES IN THE PLANNED ANALYSIS OF THE STUDY

CTP section 7.5 specifies: All patients will be followed up for relapse [...]. Any patient who has not relapsed will be censored in the analysis of the primary endpoint at the time of last patient contact. In fact, the primary endpoint analysis is the ITT analysis, which is indicated in CTP section 7.3 to include relapses only during the 28-week planned on-treatment period. See Section 6.6 for corrections.

The following additional analyses, which were not mentioned in the CTP, were added:

- Time to Discontinuation was added as a further endpoint.
- Time to Treatment Discontinuation or Relapse was added as a sensitivity analysis to the primary endpoint

Recruitment to this study was stopped early by the Sponsor due to slow enrolment. As a result, statistical power is reduced because of sample size reduction, analyses remain the same as planned, see more details in Section 7.4. A fast-track approach will be taken in order to expedite decision making and for preparation of the planned phase III trials, see more details in Section 9.2.

Details surrounding the planned assessment of the impact of the COVID-19 pandemic on the trial, are specified in section 9.3.

Hazard ratio calculated from the Cox proportional hazard model and a 95% confidence interval around the HR will be provided for primary and secondary endpoint; relative risk reduction and a 95% confidence interval around the RRR will be provided for further endpoints.

Due to the fact that there were cases where the site was not able to enter the data into the iPad in a timely manner and was unable to confirm with the site the actual date the assessment was completed, visit start date as recorded on the CRF will be used as the analysis date. Confirmed that all assessments started on the visit date and therefore it is a reasonable assumption to use the CRF recorded visit date as the analysis date.

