6.6 HANDLING OF MISSING DATA AND OUTLIERS

Assessment of relapse data (primary endpoint):

All patients will be followed up for relapse [...]. Any patient who has not relapsed will be censored in the analysis of the primary endpoint at the time of their planned complete 28-week treatment period. This does not include the T/W period. For AEs that meet the primary endpoint criteria, missing or incomplete AE dates are imputed according to BI standards.

The sensitivity analysis will use the Full Follow-up period to demonstrate the robustness of the results of the main analysis. See revised CTP Section 7.3

PANSS positive symptoms (key secondary analysis)

Change from baseline in PANSS positive symptoms will be evaluated using Mixed effect Model for Repeated Measures (MMRM) approach. This approach allows for missing data, assuming they are missing at random. All patients can be included in the model and missed visits will not be imputed. If a PANSS item is missing, the missing score on that individual PANSS item will not be imputed; if individual PANSS item is missing within a PANSS subscale, this subscale cannot be included in the calculation of the overall PANSS total score. Therefore, patients with missing individual PANSS items will also have a missing PANSS total score at that visit. However, subscale scores will be used for analysis if none of the individual items are missing.

Relative Risk Reduction (RRR)

Per revised CTP Section 7.5.:

All patients in the FAS will be included [...] *regardless of drop-out.*

For

AE dates

Missing or incomplete AE dates are imputed according to BI standards (see "Handling of missing and incomplete AE dates") (3).

PK data

Missing data and outliers of PK data are handled according to Reference (2) and as described in Section 10 of the revised CTP.

In December 2019, during the conduct of the trial, a Visit 8 eCRF page was added to capture
the date and time of the last dose of BI drug intake before the PK sampling performed at Visit
8. For patients who had completed the trial at that time, or patients for whom the visit 8 date
had passed, the data will be used to inform the date and time of the last BI drug
intake.
Sensitivity analysis: the date and time of the last dose of BI drug intake at Visit 8 collected in
the eCRF will be compared to the information recorded in This will be done for

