7.5.2 (Other) Secondary endpoint(s)

Secondary endpoints will be analyzed as described in section 7.3.2 in the revised CTP:

Time to change in antipsychotic medication will be analysed in the same manner as the primary endpoint using the stratified Cox proportional hazards model.

Additionally, the analyses for suicidal ideation and behaviour as assessed by C-SSRS will be analysed by calculating a relative risk reduction and providing a 95% confidence interval around the RRR.

The following SAS code will be used for RRR:

```
proc freq data=patdata;
  tables trtp*avalc /chisq RELRISK;
  ods output
RelativeRisks=rr(where=(lowcase(STUDYTYPE)='Cohort (Coll Risk)')
rename=(value=compestimate lowercl=complower uppercl=compupper))
ChiSq=chi(where=(lowcase(STATISTIC)='chi-square') rename=prob=comppvalue);
run;
```

The PGI-I score, change in CGI-S and PSP will be summarized descriptively.

For the secondary endpoints summary, the worse case scenario data will be analyzed if multiple assessments are completed during the same visit window.

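### The C-SSRS suicidality RRR ignores how long each patient was observed, so unequal loss of C-SSRS follow-up between arms can bias it; state the coding and add an observation-time analysis

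*Protocol*

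**What the plan says.** - **Denominator.** Protocol 7.5 sets the rule for RRR analyses: "all patients in the FAS will be included in the calculation of the RRR, regardless of dropout". SAP 6.6 carries it over: "All patients in the FAS will be included".
- **Endpoint and estimator.** Under Secondary analysis, Protocol 7.3.2 has C-SSRS suicidal ideation and behaviour "analysed by calculating a relative risk reduction and providing a 95% confidence interval around the RRR". SAP 7.5.2 repeats this, and its code is "tables trtp*avalc /chisq RELRISK": a plain two-by-two table without time at risk.
- **Analysis set.** In Protocol 7.3 the FAS "includes all patients in the treated set with at least one post-baseline measurement of any type". SAP 6.3 also asks for a baseline measurement. Neither requires a post-baseline C-SSRS.
- **C-SSRS collection.** It is an interview at each clinic or phone visit, covering the time since the previous one (Flow Chart; Protocol 5.2.5.1). After early drug discontinuation (Protocol 3.3.4.1 and 6.2.2), Option 1 keeps the regular visits and Option 2 keeps C-SSRS by phone. Options 3 and 4 end scheduled C-SSRS after the EOT and follow-up visits; only psychiatric illness or relapse and vital status are sought at about week 28. Withdrawal of consent and loss to follow-up also end collection.
- **Effect measure.** SAP 4 says a hazard ratio with "a 95% confidence interval around the HR will be provided for primary and secondary endpoint", and that "relative risk reduction and a 95% confidence interval around the RRR will be provided for further endpoints". SAP 7.5.2 nevertheless assigns an RRR to C-SSRS, which is a secondary endpoint.

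**The concern.** A crude proportion treats every patient as observed for the full 28 weeks. C-SSRS events are found only at interviews, so a patient whose interviews stop early has less chance to show one. If that patient stays in the denominator with no event, the arm with more lost observation has its risk understated. The relapse endpoint has detailed at-risk dates in SAP 7.4.1; the C-SSRS endpoint has none.

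Suicidality is a secondary endpoint and also a named safety concern: Protocol 1.4 says an effect of this centrally acting compound cannot be ruled out. Greater loss of observation on active treatment would push the RRR towards protection and could mask harm. Greater loss on placebo would do the opposite.

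**Working it through.** **The plan's own figures.** The documents give no expected rate, power or sample size for the suicidality RRR. The check borrows 258 pooled active patients, 129 placebo patients and 20% overall dropout from Protocol 7.7. The 74 events stated there reproduce: (1.960 + 0.842)² / [(1/3)(2/3)(ln 0.5)²] = 73.5, rounded up to 74.

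**Assumptions.**
- Dropout by arm is assumed, since only the overall 20% is given.
- The 28-week suicidality risk p is assumed between 3% and 10%. As a marker, Protocol 1.2 reports suicidal ideation in 3.6% of placebo patients in trial 1289.6, a 12-week study. At a constant hazard that is 1 − (1 − 0.036)^(28/12) = 8.2% over 28 weeks.
- Loss of C-SSRS is steady over time and unrelated to suicidality.
- The true risk ratio is 1.

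**Formula.** With l = −ln(1 − p) and d = −ln(1 − dropout), the probability of an observed event when C-SSRS stops at dropout is

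R = l/(l + d) × [1 − exp(−(l + d))].

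Example with p = 5%, so l = 0.0513:
- placebo dropout 15%: d = 0.1625, R = 0.0462
- active dropout 25%: d = 0.2877, R = 0.0435
- crude RR = 0.0435 / 0.0462 = 0.94

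If half of the dropouts continue C-SSRS, each arm's risk becomes 0.5R + 0.5p, and the RR is 0.97.

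| Dropout, placebo / active | RR, none assessed further | RR, half continue | RR, all continue |
|---|---|---|---|
| 15% / 25% | 0.94 | 0.97 | 1.00 |
| 15% / 30% | 0.91 | 0.96 | 1.00 |
| 10% / 35% | 0.86 | 0.93 | 1.00 |
| 30% / 15% | 1.10 | 1.04 | 1.00 |
| 20% / 20% | 1.00 | 1.00 | 1.00 |

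The values hardly change for p from 3% to 10%.

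**Sensitivity to timing.** Very early loss is worse. If all dropouts left right after the first post-baseline measurement, the RR would be (1 − active dropout)/(1 − placebo dropout): 0.75/0.85 = 0.88 for 15%/25%, and 0.65/0.90 = 0.72 for 10%/35%.

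**Counting observation time.** Expected person-time per patient is [1 − exp(−(l + d))]/(l + d). Dividing R by it returns l in both arms, so the rate ratio is 1.00 whatever the dropout split, provided that loss is unrelated to suicidality.

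**Size against noise.** At no true effect, SE(ln RR) = √[(1 − p)/(129p) + (1 − p)/(258p)]. At p = 3.6% this is √(0.2076 + 0.1038) = 0.558, giving a 95% interval for the RR of 0.33 to 2.99. At 8.2% it is 0.49 to 2.03. For dropout differences of 10 to 20 points under steady loss, the chance of a significant result in the spurious direction is at most about 6%, against 2.5% without bias.

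**The case against.** The main points on the other side are these.

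1. **No rule says that patients who leave early are event-free.** The explicit no-event assumption in Protocol 7.3.1 covers relapse only. PROC FREQ as written drops patients with a missing outcome, which would break the all-FAS rule in the other direction. The public SAP 6.6 breaks off just after the RRR rule, so withheld text may settle it. This stands: event-free coding is an inference. The all-FAS rule points that way, and the coding needs stating in either case.
2. **Stopping drug is not losing C-SSRS.** A reader might infer that any difference in discontinuation, say for visual adverse events, appears as a suicidality effect. The documents do not support that. Options 1 and 2 continue C-SSRS. Under Options 3 and 4, a patient stopping at week 4 is still due an EOT visit within 7 days and a follow-up visit 28 days later, so C-SSRS reaches about week 8 or 9 (8/28 to 9/28, or 0.29 to 0.32 of the period). One seventh applies only to a patient who disappears at week 4. Protocol 4.1.2 also describes tolerability at both doses as similar to placebo, so greater loss on active treatment is not documented.
3. **SAP 4 might seem to require a hazard ratio here already.** It does not. A Cox model cannot apply to CGI-S, PGI-I or PSP, which are also secondary endpoints. The sentence is loose, most naturally meant for time to antipsychotic change, and needs tidying.
4. **Stakes are limited.** The endpoint is descriptive and outside the testing hierarchy. Suicidal behaviour and type 4 or 5 ideation also enter the primary composite and must be reported as SAEs. This stands.
5. **A time-to-event analysis has its own weaknesses.** It changes the estimand from status over 28 weeks to time to first event. At 3.6%, 129 placebo patients give about 5 events (129 × 0.036 = 4.6), across six countries listed in SAP 5.4.1, so a country-stratified Cox model may not be estimable. Censoring at the last C-SSRS assumes that leaving is unrelated to suicidality, which is open to doubt. For the same reason, the lack of country strata in the crude table is not a defect. These points shape the fix but do not remove the need for it.

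**Conclusion.** The concern holds in a limited form. The crude all-FAS RRR takes no account of C-SSRS observation time. If incomplete follow-up is coded as no event, unequal loss of C-SSRS observation moves it towards apparent protection in the arm that loses more. Under steady loss and no true effect, the RR is about 0.94 to 0.86 for the assumed splits of 15%/25% to 10%/35% when no dropout is assessed further. That is the ceiling for those splits under steady loss. The shift roughly halves if half continue and is nil if all continue or loss is equal.

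This is modest beside a null interval of about 0.33 to 2.99 at planned numbers, and SAP 4 reports that recruitment stopped early, so the real interval will be wider. All arm-specific dropout rates are assumptions. Loss related to suicidality could give a larger or opposite bias, and the documents offer no figure for it. The change is still worth making: it concerns a named safety question and uses data already collected.

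**What to change.** 1. In SAP 7.5.2, state how the C-SSRS outcome is set for patients with incomplete or no post-baseline C-SSRS, and make the code agree with the all-FAS rule. Keep the crude RRR as a descriptive line.
2. Add time to first post-baseline C-SSRS suicidal ideation or behaviour over the ITT period, censored at the last C-SSRS. Show Kaplan-Meier cumulative incidence at week 28 by arm, with a hazard ratio or an exposure-adjusted rate. Leave it unstratified if events are too few for country strata.
3. Report C-SSRS observation time by arm, and state that the analysis assumes censoring unrelated to suicidality.
4. Reword SAP 4 so that its assignment of hazard ratio and RRR agrees with SAP 7.5.2.

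The cost is one extra analysis and some SAP wording, with no new data. The downside is a wide and possibly unstable estimate, because events will be few.
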